3.1 General Design

This is a prospective observational study of patients with normally functioning (competent) and diseased (incompetent) BAVs. Patients will be stratified into two groups based on degree of baseline aortic insufficiency. Those patients with less than moderate (+2) AI will be in the “competent BAV” group, and those patients with greater than moderate (+2) AI will be in the “incompetent BAV” group. Each group will be limited to 30 patients. All patients will follow the same study time course and undergo the same study procedures, including an annual 4D CTA scan. The goal of this work is to describe differences in the anatomical and functional characteristics of BAVs in these two groups based on 4D CTA.

Overview of study procedures (described in Section 5):

- Screening for study eligibility and informed consent
- 4D CTA imaging at baseline and at 1-year intervals over a period of 5 years. (Annual CTA studies will be performed routinely in some or many of the patients, but the 4D protocol will be for research purposes.)
- Annual office visits and echocardiography studies over the 5-year study period (standard of care)

3.2 Study Measures

Image-derived measures of BAV morphology and dynamics

Features of BAV morphology and motion will be extracted from 4D CTA images acquired at baseline and at 1-year intervals over a period of 5 years. Manual and automated segmentation and deformable modeling algorithms similar to those presented in (Pouch et al., 2012) and (Pouch et al., 2015) will be used generate a 4D model of the BAV apparatus in each 4D CTA scan, which will depict BAV morphology and dynamics over one complete cardiac cycle. The measures extracted from each model will include, but are not limited, to the following:

- Cusp surface areas over the cardiac cycle
- Cusp height (geometric and effective)
- Cusp free margin length
- Cusp thickness (including raphe thickness, if applicable)
- Commissural height
- Characteristics of cusp fusion (e.g., symmetric cusp geometry or cusp fusion angle for asymmetric valves)
- Aortic root dimensions (e.g., sinotubular junction diameter/area, sinus of Valsalva diameter/area, aortic annular geometry, ventriculoaortic junction diameter/area, root volume)
- Coaptation height at diastole
- Cusp displacement over the cardiac cycle
- Cusp velocity/acceleration over the cardiac cycle
- Geometry of the ascending aorta (e.g., aortic size)

Measures from office visits, imaging studies, and interventions

Relevant measurements will be recorded from annual office visits, other routine cardiac imaging studies (e.g., echocardiography or MRI), and interventions such as cardiac surgeries performed during the study period. These will include, but are not limited, to the following (all are collected as standard of care):

- Physical exam measurements and vital signs (e.g., height, weight, pulse)
- Severity of AI or AS (assessed on routine echocardiography)
- Measurements from other routine images (e.g., echocardiography or MRI) complementary to the 4D CTA measures listed above
- Physical intraoperative measurements, such as cusp height (if an aortic surgery is performed during the study period)

CONFIDENTIAL

2011 to June 2018, one surgeon at our center performed aortic valve replacement on 344 patients with BAV. Many more have undergone repair or have only been followed with routine echocardiogram and CT scans as they have not yet met the indications for surgery.

We will primarily use PennChart to identify patients scheduled in our cardiology and cardiac surgical clinics who have been diagnosed with BAV. Additionally, we will be identifying patients who receive an echocardiogram at Penn and are noted to have a BAV. After identification and screening via chart review, patients will be approached by a research coordinator, either in person (in clinic, heart and vascular testing center, or inpatient wards) or via telephone to gauge interest and, if interested, schedule them for a visit in our research clinic to sign consents. Finally, we will be identifying patients through the Penn Biobank to screen and, if they meet criteria, contact to gauge interest and schedule for a clinic visit. Privacy of individuals will be maintained by communicating only in private spaces within the hospital or by phone.

4.6 *Vulnerable Populations:*

We will not enroll patients who are unable to provide consent themselves. Pregnant women and children are excluded from this study. Monetary compensation will not be provided for participation.

Although not directly targeted, mentally disabled persons, economically or educationally disadvantaged persons, and/or employees or students of the University of Pennsylvania will not be denied enrollment and any special protections and/or additional safeguards will be undertaken in order to protect the rights and welfare of these subjects from coercion or undue influence as appropriate.

5 Study Procedures

The procedures summarized in Section 3 are listed in Table 1.

Table 1: Schedule of Study Procedures

Study Phase	Screening	Observation Study Visits				
		1 (Baseline)	2	3	4	5
Visit Number						
Years from Baseline Study		0	1	2	3	4
Review Inclusion/Exclusion Criteria	X	X	X	X	X	X
Medical Record Review (routine office visits, imaging and laboratory studies, cardiac procedures)	X	X	X	X	X	X
Informed Consent	X					
4D CTA		X	X	X	X	X
Pregnancy Test		X	X	X	X	X
Adverse Event / Unanticipated Problems Assessment		X	X	X	X	X

CONFIDENTIAL

This material is the property of the University of Pennsylvania.

Does your study use MRI? (CAMRIS is the appropriate contact for all studies involving MRIs)

Yes No (If No, no CAMRIS review needed)

Does your study include pregnant women?

Yes No

Does your study involve the exposure to radiation, radiotracers and/or radiological imaging modalities?

Yes No (If No, no RRSC review is needed)

Will any of the radiation exposure result from procedures that are or could be performed solely as a result of a subject's participation in the research protocol?

Yes No

Ultrasound

Yes No (routine echocardiography only)

Will your study be using CT Scans? (CACTIS is the appropriate contact for studies involving CT scans)

Yes No

Studies involving Nuclear Medicine: Will subjects be undergoing any of the following procedures specific to research:

MUGA
(See Nuclear Medicine-Muga Scan)

PET/CT Scan
(See PET/CT Scan)

Bone /DXA
(See Bone Scan)

None of the above apply

Check off all of the following procedures that will be performed in your research- each option you select will link to the template language document:

Apheresis/plasma exchange

Leukapheresis

Bone Marrow Biopsy or Aspirate

Use of AP clinical specimens

Biopsies- check those which apply

Blood draw

None of the above apply

5.1 Screening

The screening visit for eligibility assessment will include:

- Medical record review to verify documentation of a BAV, previous aortic interventions, presence of renal failure, contraindications to contrast agents, and pregnancy status. (Note: a pregnancy test will be performed prior to each 4D CTA study.) Pregnant women will be excluded from the study if they confirm pregnancy at the time of screening or if the pregnancy test prior to baseline imaging is positive.
- Informed consent

CONFIDENTIAL

5.2 *Study Intervention or Observational Phase (Give this section a name that is relevant to the design of your study)*

5.2.1

Baseline Imaging

After being identified, screened, and have provided informed consent, all patients will undergo a baseline 4D CTA imaging study. A pregnancy test will be performed in women prior to the 4D CTA study. Each 4D CTA scan will be performed according to established TAVR imaging protocols with modifications to limit radiation dose to approximately 5 mSv.

Additional baseline information may be collected (standard of care):

- Other routine imaging studies (e.g., echocardiography or MRI)
- Physical exam
- Vital signs
- Laboratory tests, including creatinine level
- Quality of life assessments

5.2.2 *Annual follow-up imaging and visits*

After baseline imaging, patients will have annual routine clinic follow up visits (1 year \pm 90 days) that will consist of the following:

- Medical history and physical (standard of care)
- Transthoracic echocardiogram (standard of care)
- Laboratory studies, including creatinine level (standard of care)
- 4D CTA (research). As annual CT scans are often standard of care in these patients, the research component will be the additional 4D imaging protocol, performed according to established TAVR imaging protocols with modifications to limit radiation dose to approximately 5 mSv.

5.3 *Unscheduled Visits and Surgeries*

Medical information and image data collected as standard-of-care at visits other than the scheduled annual follow-up may be included in the patient's research record. For example, relevant information from cardiac imaging studies or office visits other than the annual follow-up will be documented, especially as it relates to the development of AI and/or AS and associated symptoms. If a patient requires aortic valve repair or replacement during the 5-year study period, information that is routinely acquired during the operation will be recorded (e.g., procedures performed, prosthetic devices used, pre- and post-operative imaging and exam measurements, etc.).

5.4 *Subject Withdrawal*

Subjects may withdraw from the study at any time without impact to their care. They may also be discontinued from the study at the discretion of the Investigator for lack of adherence to study procedures or visit schedules. Patients will be followed for any safety events. If a patient meets the indications for valve surgery during their participation in the study, they will remain in the study on their original study timeline, unless they require an aortic valve replacement, at which point they will end their study participation. It will be documented whether or not each subject completes the study.

CONFIDENTIAL

6 Statistical Plan

6.1 Sample Size Determination

The sample size for this study is based on our previous work on automated heart valve analytics in 3D transesophageal echocardiography, wherein a minimum of 20 patients was needed to develop and evaluate the accuracy of semi-automated methods for reconstructing the mitral valve and tricuspid aortic valve apparatus in 3D images and to derive anatomical valve features similar to those described in Section 3.2 (Pouch et al. Media 2014; Pouch et al. Media 2015). Similar to the 4D CTA analysis proposed in this study, we used those image analysis techniques to carry out a statistical shape analysis of physiologically normal mitral annular geometry (Pouch et al., ATS 2014), as well as a comparison of normal vs. myxomatous valve morphology (Pouch et al., 2016), also with ~20 subjects per group. In this protocol, we propose to enroll 30 subjects in both the “competent BAV” and “incompetent BAV” groups; we anticipate this is the number needed to ensure that we obtain adequate image data from at least 20 subjects in each group given the potential for suboptimal image quality or patient withdrawal. Based on our previous work, 20 patients per group is likely the minimum necessary as a starting point to demonstrate feasibility of BAV modeling in 4D CTA data.

6.2 Data Analysis

6.2.1 Baseline Data

Baseline and demographic characteristics will be summarized by standard descriptive statistics (including mean and standard deviation for continuous variables such as age and standard percentages for categorical variables such as gender).

6.2.2 Analysis of Primary Outcome of Interest

Post-processing of each 4D CTA data set will involve manual or semi-automatic image segmentation (labeling) and geometrical modeling of the BAV at each cardiac phase. Geometrical and functional measurements (e.g., coaptation area, coaptation height, cusp surface area, aortic root diameters, valve orifice area, localized cusp thickness, and aortic cusp and root velocities) will be extracted from the 4D CTA image segmentations to quantify valve morphology and dynamics at each study time point, as well as longitudinally. Measurements from the competent and incompetent BAV groups will be reported with standard descriptive statistics, including group means and standard deviations time-normalized with respect to the cardiac cycle at each study time point. Comparison of valve measurements in the two groups will be carried out with independent Student t-tests at multiple phases of the cardiac cycle with false discovery rate adjustment to account for multiple comparisons. We will perform additional statistics on longitudinal data. Comparable measurements will be made on standard-of-care echocardiography and/or MR image data when available.

7 Safety and Adverse Events

Potential safety issues in this study are related to radiation and contrast for the 4D CT exam. An internal safety committee, including representation from Radiology and Cardiothoracic Surgery, will monitor for adverse events. All CTs will be reviewed on a quarterly basis concerning radiation dose. Moderate to severe contrast reactions will be reported to the IRB as severe adverse events and evaluated individually by the safety committee. Patients who have severe adverse events will be withdrawn from the study. Mild reactions to contrast will be reviewed quarterly to evaluate whether the participant should continue in the trial.

8 Study Administration, Data Handling and Record Keeping

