Intervention	
The study involves annual 4D CTA imaging of the bicuspid aortic valve for a period of 5 years. CTA is often standard of care for BAV patients, but patients in this study will receive a higher radiation dose with a 4D imaging protocol. There may also be patients enrolled in the study who have a 4D CTA for research purposes when a routine CTA is not required for clinical care.

Statistical Methodology	
Patients will be stratified into “competent” and “incompetent” BAV groups based on the severity of aortic insufficiency on routine echocardiography at the time of study enrollment. Geometrical and functional measurements (e.g., coaptation area, coaptation height, cusp surface area, aortic root diameters, valve orifice area, localized cusp thickness, and aortic cusp and root velocities) will be extracted from each 4D CTA scan to quantify valve morphology and dynamics at each study time point, as well as longitudinally. Measurements from the competent and incompetent BAV groups will be reported and compared.

Data and Safety Monitoring Plan	
The PI will be responsible for the data quality management and the ongoing safety of subjects.

Background and Study Rational

1 Introduction

The bicuspid aortic valve (BAV) is the most common congenital heart disease. The purpose of this study is to better understand the anatomy of physiologically “normal”, or competent, BAVs without stenosis or insufficiency (AI) in order to support evidence-based standardization of BAV repair surgery. Men and women over 18 years of age with a diagnosis of BAV and minimal aortic valve calcification at baseline will undergo annual 4D computed tomography angiography (CTA) scans, transthoracic echocardiograms, and history and physical assessments over the course of the 5-year study period. Patients who are pregnant, have renal insufficiency (creatinine > 2 mg/dL), or who have a contraindication to intravenous contrast will be excluded. Patients will be stratified into study groups according to baseline AI: approximately half of patients will have no to mild AI at baseline and the other half will have moderate to severe AI at baseline. Anatomical measurements will be obtained from the 4D CTA scans and analyzed at each phase of the cardiac cycle, as well as longitudinally. The 4D CTA imaging and analysis will not

CONFIDENTIAL

This material is the property of the University of Pennsylvania.

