8.1 Confidentiality

CONFIDENTIAL

Information about study subjects will be kept confidential and managed according to the requirements of the Health Insurance Portability and Accountability Act of 1996 (HIPAA). Those regulations require a signed subject authorization informing the subject of the following:

- What protected health information (PHI) will be collected from subjects in this study
- Who will have access to that information and why
- Who will use or disclose that information
- The rights of a research subject to revoke their authorization for use of their PHI.

In the event that a subject revokes authorization to collect or use PHI, the investigator, by regulation, retains the ability to use all information collected prior to the revocation of subject authorization. For subjects that have revoked authorization to collect or use PHI, attempts should be made to obtain permission to collect at least vital status (i.e. that the subject is alive) at the end of their scheduled study period.

All image data and non-image patient information will be associated with a study-specific subject ID. The link between the subject ID and patient identity will be maintained in a RedCap form that will only be accessible to the PI and designees. The data files (medical images and patient characteristics) used for offline analysis will be de-identified and associated with the study-specific patient ID, not a patient name or other PHI. These data files will be stored on a password protected NAS server, stored in a locked Penn clinical research facility, accessible only to authorized personnel only through the UPHS network and will be independent of the RedCap form. Date-shifting will be used to ensure confidentiality, and the date shifting scheme will be stored only in the RedCap form. Any data shared with other investigators will be de-identified and void of both direct and indirect identifiers. If data transport is necessary, only UPHS-approved devices will be used.

8.2 *Data Collection and Management*

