A link between the patient's medical record, name, and study-specific subject ID will be recorded in a RedCap form to which only the PI and designees will have access during the study. Images and electronic data forms containing PHI will be stored on computers or servers managed by the University of Pennsylvania Health System. When saving raw image data from the CT scanners, hospital-approved encrypted hard drives will be used for data transport. All papers with patient related study data (such as inclusion/exclusion forms, ICFs, imaging reports) will be stored in a locked binder closet within the Thoracic Aortic Surgery Program offices located at [name].

All PHI will be stored in RedCap. The PHI will include name, medical record number, date of birth, encounter dates, and the randomly generated number by which all that patient's dates in the database are shifted. Images will be anonymized and stored on a password protected NAS server, stored in a locked Penn clinical research facility, accessible only to authorized personnel only through the UPHS network. Any image data exported from the NAS server will be de-identified. Patient factors exported from the RedCap database for analysis will not include patient identifiers, such as patient name or MRN. The patient's date of birth and all encounter dates will be time-shifted by the same number of days in a range between -60 and -5. The date-shift value will be randomly generated and stored in the RedCap form that will link the patient's PHI to their study-specific ID. No published or presented materials will identify subjects by names or initials.

8.3 *Records Retention*

The link between the patient's medical record and subject ID will remain accessible in RedCap only to the PI and designees after completion of the study. The purpose of maintaining this link is if additional examination of the record is necessary to complete data entry, or if in a future follow-up study additional

CONFIDENTIAL

This material is the property of the University of Pennsylvania.

information from the medical record may be needed to test future hypotheses. The PI will not access identifiable data for a future research study without prior IRB approval.

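### The protocol does not require readers who segment the 4D CTA scans to be masked to AI group, and its de-identification steps do not supply that masking

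*Protocol*

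**What the plan says.** **How the measurements arise.** Protocol Section 6.2.2: "Post-processing of each 4D CTA data set will involve manual or semi-automatic image segmentation (labeling"), followed by geometric modelling at each cardiac phase. The geometric and functional measures are then extracted from those segmentations. Section 3.2 words the method a little differently: "Manual and automated segmentation and deformable modeling algorithms similar to those presented in" the group's published work.

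**How the groups arise.** The Study Summary stratifies patients into competent and incompetent groups "based on the severity of aortic insufficiency on routine echocardiography at the time of study enrollment". Section 3.1 does the same by degree of baseline AI.

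**How the groups are compared.** Section 6.2.2 plans "independent Student t-tests at multiple phases of the cardiac cycle with false discovery rate adjustment to account for multiple comparisons".

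**What is done to the files.** Section 8.1: "The data files (medical images and patient characteristics) used for offline analysis will be de-identified and associated with the study-specific patient ID". It gives the purpose of the date shift: "Date-shifting will be used to ensure confidentiality". Section 8.2: "Images will be anonymized and stored on a password protected NAS server". It also says that a patient's birth date and all encounter dates move by one common number of days, between -60 and -5.

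The protocol does not say who segments the scans, what those people may know, or in what order they read.

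**The concern.** A person traces or corrects the valve model, at least in part. That person's judgement enters measures such as coaptation height, and for coaptation the expected direction is obvious: less of it in a valve that leaks. If the reader knows the AI grade, small decisions at uncertain borders can lean that way. If manual work were used more in one group than in the other, method would also be mixed up with group.

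The comparison is not randomised, and group is known before any scan is traced. Masked reading is the direct safeguard against such expectation. The planned analysis cannot repair its absence, since false discovery rate adjustment deals with the number of tests and not with a shifted estimate. Section 10.2 hopes that the data will inform cusp height thresholds for surgical decisions, so a shift in the competent-group means could carry into reference values.

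**Working it through.** **Step 1. Do the privacy measures already mask the reader?** Three facts, side by side:

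- Section 8.1 lists images and patient characteristics together as the files for offline analysis, under the same study ID. Removing the name does not separate the scan from information that could show the group.
- Section 8.2 uses one shift s per patient. For two visits at times t1 and t2, the shifted gap is (t2 + s) − (t1 + s) = t2 − t1. Order and spacing survive wherever dates accompany the data.
- Section 8.1 keeps the analysis files apart from the REDCap form, but that form is described as holding the identity link and the date-shift scheme. Nothing says that the AI grade is kept from readers.

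So masking neither follows from these steps nor is excluded by them.

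**Step 2. What would a reader shift do?** No figure in the plan bears on this, so there is none to reproduce. Section 6.1 gives only 30 enrolled per group, to leave at least 20 with adequate images. The protocol states no alpha, SD or effect size.

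Inputs:
- n = 20 or 30 per group (Section 6.1).
- Two-sided alpha 0.05, one test, no false discovery rate step (assumed).
- No true difference (assumed).
- b = difference between groups in mean reader error, in within-group SD units (assumed, shown as a range).

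The expected observed difference is the true difference plus b. The t statistic then follows a noncentral t distribution with df = 2n − 2 and noncentrality b × √(n/2). The rejection probability is P(|T| > t_crit), with t_crit = 2.024 for df = 38 and 2.002 for df = 58.

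| Assumed b (SD) | Noncentrality, n = 20 | Error, n = 20 | Noncentrality, n = 30 | Error, n = 30 |
|---|---|---|---|---|
| 0 | 0 | 5.0% | 0 | 5.0% |
| 0.1 | 0.316 | 6.1% | 0.387 | 6.7% |
| 0.2 | 0.632 | 9.5% | 0.775 | 11.9% |
| 0.3 | 0.949 | 15.2% | 1.162 | 20.8% |
| 0.5 | 1.581 | 33.8% | 1.936 | 47.8% |

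The error grows with n because a larger sample estimates the biased difference more precisely.

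**Step 3. Scale where a true difference exists.** The shift still adds b to the estimate. With 80% power, the same test detects about 0.91 SD at n = 20 and 0.74 SD at n = 30. A shift of 0.2 to 0.3 SD is 0.2/0.91 = 22% to 0.3/0.91 = 33% of the first, and 0.2/0.74 = 27% to 0.3/0.74 = 41% of the second.

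**The case against.** The strongest reply is that the protocol is silent, and silence is not a statement that readers are unmasked. Only the protocol is at hand, and a reading procedure may exist elsewhere. This stands as a limit on wording: the point is that masking is not required, not that it is absent. It does not dispose of the point. The protocol itself describes segmentation and file handling, and what readers know is study conduct that no later analysis can restore.

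Other objections also stand in part:

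- **Masking would be incomplete.** A coaptation defect may show the group (an inference; the protocol does not discuss it). Under Section 5.4, patients who have a valve repair remain in the study, so a later scan may reveal surgery.
- **Shuffling across all visits would be slow.** Table 1 places scans at years 0 to 4. Holding baseline scans until later ones exist would delay the baseline comparison and the feasibility aim of Section 6.1. The fix should not demand it.
- **The error rates are hypothetical.** The shifts and the 5% level are assumed, and one unadjusted test is not the planned analysis. The study is largely descriptive, and no true difference is least plausible for coaptation itself.

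A reader might also infer that the scans carry nothing but a study ID, so that masking costs nothing; that every primary measure is affected; that the group is assigned by the same people who trace; or that manual or semi-automatic work is chosen scan by scan. The documents support none of these. Characteristics share the ID, Section 3.2 also mentions automated segmentation, and neither the readers, the people who assign group nor the rule for choosing the method is described.

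**Conclusion.** The point holds in a limited form. The protocol leaves an operator-dependent, non-randomised comparison without a requirement that readers be masked to AI group, and its privacy steps do not provide one. Bias is possible in those measures where a person's judgement enters, to a degree that depends on how much of the work is manual.

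Its size is unknown. On the assumptions above, a shift of 0.2 to 0.3 SD takes the error of a single test from 5% to about 10–15% with 20 per group or 12–21% with 30. These figures show what such a shift would do, not that one is likely. If masking removed the shift entirely, the rate would return to 5%. The sample size does not change. This is a cheap improvement that should be made, not a flaw that invalidates the design.

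**What to change.** Add to Section 6.2.2:

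1. The same readers segment scans and correct models while masked to AI grade and echocardiography results.
2. Scans carry codes that show neither group nor visit. The two groups are mixed in random order within each reading batch.
3. AI grade and patient characteristics are withheld from readers until that batch's measurements are locked.
4. The choice between manual and semi-automatic segmentation is made without reference to group.
5. Baseline scans are read in mixed-group batches without waiting for later visits. For longitudinal comparisons, visit number is masked where feasible.

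**Cost.** No extra patients, scans or visits. There is recoding work, a key to be held apart from the readers, and a short delay while each batch fills. Masking stays imperfect where a coaptation defect or a prior repair can be seen on the scan.

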BAV patients who present with AI typically range in age from 20 to 50 years old and, based on age at presentation, will survive several decades after intervention (Boodhwani et al. 2010). While aortic valve replacement is the conventional treatment for AI, it is not an ideal intervention in younger patients with non-stenotic BAVs. Bioprosthetic valves have limited durability in this patient population and will require at least one additional valve replacement over the patient’s lifetime (Aicher et al. 2011). Mechanical valves carry the risk of thromboembolic events and require life-long anti-coagulation, which limits quality of life in young patients (Salem et al. 2004). Therefore, BAV repair has become more widely adopted by surgeons in major cardiac centers in recent years, as early results have been satisfactory (Aicher et al. 2011, Svensson et al. 2014). However, repair strategies have not been standardized and are limited to single-center reports in relatively small patient series. Furthermore, techniques to determine repairability of a BAV have been adopted from normal trileaflet aortic valve studies (Schäfers et al. 2013) and there are no existing research studies of functionally normal BAV characteristics, such as coaptation height and cusp height. Such studies would help to standardize BAV repair procedures, as they would define the anatomical and dynamic valve characteristics that are needed to recreate BAV competence during valve repair surgery.

The goal of this research is to characterize the aortic valve and root geometry/dynamics of physiologically normal BAVs relative to BAVs with moderate to severe AI. While transesophageal echocardiography (TEE) is the most commonly used imaging modality to assess valve morphology and dynamics, it requires sedation and is not typically ordered for routine annual surveillance. In this study, 4D computed tomography angiography (CTA) imaging will be used to analyze aortic cusp motion and coaptation and to create four-dimensional BAV models to measure aortic root landmarks and valve characteristics over the cardiac cycle. The long-term goal of this research is to follow the natural history course of BAV syndrome and the development of AI or AS.

2 Study Objectives

2.1 *Primary Objective*

- To use medical imaging to determine the anatomical parameters (e.g., aortic valve and aortic root dimensions and dynamics) for BAV competence.

2.2 *Secondary Objectives (if applicable)*

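### Section 6.2.2 compares groups formed by observed AI grade with unadjusted t-tests; if the groups differ in body size, sex or age, a raw difference in dimensions or motion cannot be read as a parameter of competence

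*Protocol*

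**What the plan says.** - **Groups.** Protocol section 3.1 describes a prospective observational study: "Patients will be stratified into two groups based on degree of baseline aortic insufficiency". It states the goal as describing how the two groups differ.
- **Objective.** Section 2.1 goes further: "To use medical imaging to determine the anatomical parameters (e.g., aortic valve and aortic root dimensions and dynamics) for BAV competence". The Introduction and section 10.2 expect the measurements to inform future standards for repair candidacy, including cusp-height thresholds.
- **Measures.** Section 3.2 lists mainly absolute lengths, areas and volumes, for example "Aortic root dimensions (e.g., sinotubular junction diameter/area, sinus of Valsalva diameter/area, aortic annular geometry, ventriculoaortic junction diameter/area, root volume", together with motion measures such as "Cusp displacement over the cardiac cycle" and cusp velocity and acceleration.
- **Test.** Section 6.2.2: "Comparison of valve measurements in the two groups will be carried out with independent Student t-tests at multiple phases of the cardiac cycle". False discovery rate control is the only adjustment. The only normalisation is of cardiac-cycle time: "including group means and standard deviations time-normalized with respect to the cardiac cycle at each study time point".
- **Candidate covariates.** Section 3.2 commits to collection ("Relevant measurements will be recorded from annual office visits") and lists "Physical exam measurements and vital signs (e.g., height, weight, pulse"). Section 5.2.1 describes the baseline physical examination as optional. Section 6.2.1 summarises age and gender descriptively. The text at hand gives none of these a role in the group comparison.

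**The concern.** AI grade is observed, not assigned, and the study admits adult men and women with no upper age limit in the listed criteria. Body size, sex and age can therefore differ between the groups, and lengths, areas, volumes and displacements can vary with all three. If the incompetent group happens to be larger or more often male, the named test can report bigger roots and cusps as features of incompetence. The opposite imbalance can hide a real difference. False discovery rate control does not help, because it addresses multiplicity and not bias. At stake is what may be concluded about the primary objective, and later about thresholds meant to guide repair.

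**Working it through.** **Inputs from the protocol.** Section 6.1 plans 30 enrolled per group to leave at least 20 with adequate images. It gives no alpha, power, SD, effect size or covariate distribution, so there is no power figure to reproduce.

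**Assumed inputs.** Two-sided 5% test; within-group SD of the measure = 1; body-size imbalance D (in SD) and within-group correlation r of body size with the measure. Low: D = 0.3, r = 0.3. Mid: 0.5, 0.5. High: 0.8, 0.6.

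**1. Spurious difference.** With no group effect given body size, the raw means differ by r × D:
- low: 0.3 × 0.3 = 0.09 SD
- mid: 0.5 × 0.5 = 0.25 SD
- high: 0.6 × 0.8 = 0.48 SD

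**2. Rejection rate of the t-test.** Noncentral t with 2n − 2 degrees of freedom and noncentrality r × D × √(n/2).

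| n per group | balanced | low | mid | high |
|---|---|---|---|---|
| 20 | 5.0% | 5.9% | 12.0% | 31.6% |
| 30 | 5.0% | 6.4% | 15.9% | 44.8% |

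The bias r × D does not depend on n, so a larger sample rejects more often. In simulation, the model with group, body size, age and sex rejects about 5% throughout.

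Sex imbalance acts in the same way. With an assumed male-female difference of 1 SD, 80% against 60% male gives 9% (n = 20) or 11% (n = 30); 85% against 50% gives 17% or 23%.

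**3. Hiding a real difference.** In balanced groups the t-test has 80% power at 0.909 SD (n = 20) or 0.736 SD (n = 30). An opposing imbalance leaves 0.909 − 0.09 = 0.819, 0.909 − 0.25 = 0.659 or 0.909 − 0.48 = 0.429 SD at n = 20. At n = 30 it leaves 0.646, 0.486 or 0.256 SD.

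| n per group | test | low | mid | high |
|---|---|---|---|---|
| 20 | t-test power | 71% | 53% | 26% |
| 20 | adjusted power | 79% | 85% | 87% |
| 30 | t-test power | 69% | 46% | 16% |
| 30 | adjusted power | 81% | 86% | 88% |

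**4. After false discovery rate control.** The assumed family is 8 measures (6 dimensional, 2 velocity) × 10 phases = 80 tests, under Benjamini-Hochberg at 5%. If velocities are unrelated to size, the chance of at least one false rejection with t-tests throughout is:
- n = 20: 3-5% (low), 9-11% (mid), 33-35% (high)
- n = 30: 4-5%, 13-15%, 51-54%
- balanced groups: about 3%

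**5. Which measures to adjust.** Velocity is the time derivative of displacement, so it may scale with size too. If it does, adjusting the dimensions but leaving velocities on the t-test still gives about 15% (n = 20) and 27% (n = 30) in the high case. Adjusting every measure gives about 3%.

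**6. Precision of the adjusted model.** Detectable difference at 80% power, averaged over simulated designs with age and sex balanced and unrelated to the measure:
- n = 20: 0.77-0.98 SD, against 0.91 unadjusted
- n = 30: 0.61-0.78 SD, against 0.74 unadjusted
- unfavourable case (all three covariates about 0.8 SD imbalanced, multiple correlation only 0.3): about 1.12 SD at n = 20 and 0.89 SD at n = 30

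**The case against.** The strongest reply is that the test fits the stated goal. Section 3.1 wants differences described, section 6.1 sizes the study for feasibility, and the funding is a pilot grant. A t-test answers whether raw means differ, and preferring a covariate-conditional difference is a choice of estimand. This stands for the descriptive goal, and it is why the t-tests should be kept. It does not reach section 2.1 or the intended use for repair standards, where a raw difference would be read as anatomy of competence.

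Second, covariates and indexing are often left to a statistical analysis plan, and a t-test on body-size-indexed values would still comply with section 6.2.2. That is fair: a reader might infer that the protocol excludes indexing, and it does not. What remains is that the protocol itself names an unadjusted test for the primary outcome and leaves only the longitudinal analysis open.

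Third, a reader might infer that the study has no matching. The text at hand lacks most of section 4 before 4.6, so matching or balanced recruitment there cannot be excluded.

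Fourth, a reader might infer that the comparison will be confounded. Nothing in the protocol shows that the groups will differ in body size, sex or age. Every imbalance and correlation above is assumed, and the low case is trivial.

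**Conclusion.** The point holds in a limited form. The named comparison is a valid description of raw group differences. It cannot separate parameters of competence from body size, sex or age if the groups differ in them. Under the assumed mid and high cases, false rejection of a single test is 12-32% at 20 per group and 16-45% at 30, and an opposing imbalance cuts 80% power to 53-26% and 46-16%. Under the low case the effect is negligible. These figures illustrate what could happen and do not predict this study. They do not show that the t-test is invalid or the design unsound. This is a cheap improvement, because the covariates are largely planned for collection already.

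**What to change.** In section 6.2.2, keep the unadjusted means, SDs and t-tests as description. Base conclusions about parameters of competence on a linear model at each cardiac phase with group plus baseline body surface area, age and sex. Apply it to all dimensional and motion measures, including cusp and root velocities, with false discovery rate control over the adjusted group p-values as one family. In section 5.2.1, make recording of baseline height and weight definite, in line with section 3.2.

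The text cost is a short change to the analysis paragraph and one wording alignment, with no new procedure. The statistical cost is 3 degrees of freedom and mean variance inflation of about 1.12-1.28 at 20 per group and 1.08-1.24 at 30. Precision may therefore improve or worsen, and the gain is mainly less confounding. With 20 to 30 per group, the covariate set should stay at these three.
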